Appendix I: Study Video Draft	
Appendix J: Study Advertisement Templates	

List of General Abbreviations/Terminology

AE	Adverse Event/Adverse Experience
CFR	Code of Federal Regulations
CIB	Clinical Investigator's Brochure
CIOMS	Council for International Organizations of Medical Sciences
CONSORT	Consolidated Standards of Reporting Trials
CRF	Case Report Form
CRO	Contract Research Organization
DCC	Data Coordinating Center
DSMB	Data and Safety Monitoring Board
DSMC	Data and Safety Monitoring Committee
FDA	Food and Drug Administration
FWA	Federal-Wide Assurance
GCP	Good Clinical Practice
HIPAA	Health Insurance Portability and Accountability Act
IB	Investigator's Brochure
ICF	Informed Consent Form
ICH	International Conference on Harmonization
IDE	Investigational Device Exemption
IEC	Independent or Institutional Ethics Committee
IDEO	Intrepid Dynamic Exoskeletal Orthosis
IND	Investigational New Drug
IRB	Institutional Review Board
ISM	Independent Safety Monitor
MedDRA ©	Medical Dictionary for Regulatory Activities
MOP	Manual of Procedures
N	Number (typically refers to participants)
NDA	New Drug Application
OHRP	Office for Human Research Protections
OHSR	Office for Human Subjects Research
PHI	Protected Health Information
PI	Principal Investigator
PK	Pharmacokinetics
QA	Quality Assurance
QC	Quality Control
SAE	Serious Adverse Event/Serious Adverse Experience
SMC	Safety Monitoring Committee
SOP	Standard Operating Procedure
WHO	World Health Organization

List of METRC Abbreviations/Terminology

AFIRM	The Armed Forces institute of Regenerative Medicine
AI	Associate Investigators (Site)
CDMRP	Congressionally Directed Medical Research Program
CCCS	Civilian Core Clinical Sites
CPO	Certified Prosthetist/Orthotist
DOD	Department of Defense
DOD CRM RP	DOD Clinical and Rehabilitative Medicine Program
DOD HRPO	DOD Human Research Subject Protection Office.
DOD PRORP	Department of Defense Peer Reviewed Orthopaedic Research Program
Master Consent Form	Template consent form designed for study by the MCC
Master IRB application	Template IRB application designed for study by the MCC
MCC	METRC Coordinating Center of the Consortium
MCC Study Manager	Principal site contact for Research Coordinators at sites
MTF Core Clinical Sites	Military Treatment Facilities Core Clinical
NMCS D	Naval Medical Center San Diego
O&P Tech	Orthotics and Prosthetics Technician
OETRP	Orthopaedic Extremity Trauma Research Program
PPM	Policy and Procedure Memorandum
SCC	Satellite Clinical Site
RC	Site Research Coordinator
RS	Site Research Staff
Study Number	Protocol identification number
Study Principal Investigator	Lead Investigator on a protocol
Study Protocol Committee	Protocol development
REDCap	Research Electronic Data Capture System
USAMRMC	United States Army Medical Research and Material Command
WRNNMC	Walter Reed National Naval Medical Center

PROTOCOL SUMMARY

Title: Patient Response to an Integrated Orthotic and Rehabilitation Initiative for Traumatic Injuries. The PRIORITI-MTF Study

Sponsor: DOD PRORP

Type of study: Before-after study design; participants serve as their own controls

Objectives: The primary objective of this study is to examine the benefits (and cost-benefits) of an integrated orthotic and rehabilitation program that incorporates the Intrepid Dynamic Exoskeletal Orthosis (IDEO) and the Return to Run (RTR) physical therapy regimen, but designed for scalability in the broader military environment (i.e. beyond San Antonio Military Medical Center where the program was developed).

Participants will be evaluated at baseline (T0), immediately following 4 weeks of physical therapy with the IDEO (T2), at 6 months following completion of all physical therapy (T3) and at 12 months following completion of all physical therapy (T4). **See Figure 1.**

Specific Aim #1: To assess immediate improvements in functional performance following completion of the PRIORITI program. Functional performance will be measured using well-validated assessments of speed, agility, power, and postural stability. Hypotheses to be tested include:

a. Compared to baseline (T0), functional performance will be significantly better immediately following completion of the PRIORITI program (T8)

Specific Aim #2: To assess long-term improvements in both functional performance and patient reported outcomes 1 year after completion of the PRIORITI program. Principal hypotheses to be tested include:

a. Compared to baseline (T0), functional performance will be significantly better at one year following completion of the PRIORITI program (T4)

b. Compared to baseline (T0) patient reported outcomes will be significantly better at one year following completion of the PRIORITI program (T4)

Specific Aim #3: To document patterns of device use, use of ambulatory aids, shoe wear and patient reported satisfaction associated with the IDEO. Participants will be asked about their satisfaction with comfort, cosmesis, ease of use, and durability. As this is primarily a descriptive analysis, no hypotheses will be tested.

Specific Aim #4: To assess the economic impact of the PRIORITI program by (i) measuring one-year costs associated with participation in PRIORITI and compare these costs to those projected under standard of care; and (ii) estimating lifetime cost-effectiveness of the PRIORITI program relative to standard of care. As this is primarily a descriptive analysis, no hypotheses will be tested.

Study design: The effectiveness of the PRIORITI program will be evaluated using a before-after

study design where participants serve as their own controls.

Study duration: 3 years (6 month planning and training, 10 month accrual, 12 month final follow-up, 8 month analysis and writing).

Sample size: 90 participants will be consented to participate in this study.

Number of study sites: 3 Military Treatment Facilities (MTF's).

Inclusion criteria

1. Ages 18-60
2. Currently one or more years out from a traumatic unilateral lower extremity injury at or below the knee
3. Healed fractures and able to fully weight bear
4. Evidence of either:
 - a. Weakness of ankle dorsiflexors and /or plantarflexors resulting from leg injury (defined as less than 4 out of 5 on manual muscle test)
 - b. Limited ankle dorsiflexion (< 10 degrees) and /or limited ankle plantarflexion (< 20 degrees) resulting from leg injury
 - c. Mechanical pain with loading to hindfoot/midfoot (\geq 50 mm on a 0-100 mm visual analogue scale assessing average daily pain)
 - d. Ankle or Hindfoot fusion or candidate for ankle or hindfoot fusion
 - e. Candidate for amputation secondary to ankle/foot impairment

Exclusion criteria

1. Ankle plantarflexion or dorsiflexion weakness as a result of spinal cord injury or central nervous system pathology.
2. Non-ambulatory
3. Surgery on study limb anticipated in next 6 months
4. Medical or psychological conditions that would preclude functional testing (ex. severe traumatic brain injury, stroke, renal failure, heart disease, severe anemia)
5. Neurologic, musculoskeletal or other conditions affecting contralateral extremity preventing the study of a healthy control limb
6. Unable or unwilling to participate in two 4-week PT programs
7. Pregnancy
8. Non-English speaking

Outcome measures

Physical impairment will be determined using objective performance measures of agility (4 step square test and Illinois Agility Test), strength and power (sit to stand test and timed stair ascent), speed (self selected walking speed and 40 yard shuttle run), and postural stability (single leg stance).

Levels of participation will be measured using self reported measures of return to usual major activity (work, active duty, school, home management) and the Paffenbarger Activity Scale (PPAQ) that measures participation in light, moderate and vigorous recreational or sports activities.

Patient reported function and health related quality of life as measured using the total and dimension specific sub scales of the Short Musculoskeletal Functional Assessment (SMFA).

Statistical analysis: We are interested in assessing immediate and long-term improvements in functional performance and self reported outcomes. One-sided paired t-tests will be used to test for improvements in outcomes, comparing baseline data to later outcomes. Differences in means between follow up and baseline will be reported along with 95% confidence intervals.

Analysis of costs and benefits of PRIORITI will include an analysis of costs and outcomes observed over a 12-month period as well as cost-effectiveness projected over the patient lifetime.

Safety monitoring: The Medical Monitor is responsible for monitoring serious adverse events (SAEs) as the study progresses to ensure patient safety. The Medical Monitor may convene a meeting of the DSMB to evaluate any SAEs that he/she determines require immediate attention.

Data Safety and Monitoring Board (DSMB): The DSMB is an independent body responsible for evaluating recruitment, safety and outcome data. The DSMB has the authority to stop the study based on its findings.

1. KEY ROLES

Protocol Committee- Responsible for developing a detailed study protocol, provides oversight on study progress and acts to correct deficiencies in the conduct of the study. This committee also drafts the main publications related to the study.

Steering Committee- Steering Committee is the decision making body of the Consortium and makes decisions regarding study design issues, study procedures, allocation of study resources and priorities for meeting competing demands of the Consortium and individual studies. The Steering Committee is composed of Site Investigators from each core METRC clinical center, the Department of Defense Program Officer for METRC, the orthopaedic consultants from the Army, Navy and Air Force, regional representatives of Satellite Clinical Centers, and the Director, Deputy Director, Principal Biostatistician and Principal Economist of the Coordinating Center. The Steering Committee is responsible for approving the protocol.

METRC Coordinating Center- Responsible for maintaining all study documentation, developing and maintaining the master IRB application and consent, circulating any changes to study documents including protocols, case report forms, and IRB materials to each participating center, providing daily oversight and management of study implementation, providing payment to sites for patients enrolled, performing site monitoring, data quality control and analysis of study results.

Core Clinical Sites- Responsible for the conduct of clinical studies including patient enrollment, performing study procedures, data collection and conducting study follow-up visits.

Publications Committee- Responsible for reviewing manuscripts prior to journal submission and reviewing presentations prior to presentation; for mediating and settling disputes and conflicts among study investigators over publication or presentation priorities, authorship, and any other issues related to publications or presentations; for preparing and maintaining a list of concepts for publications and preparing and maintaining a list of approved METRC publications, which shows the status of each manuscript from initiation through publication.

DSMB- Independent Data and Safety Monitoring Board (DSMB) appointed by DOD, responsible for monitoring the accumulated interim data as the trial progresses to ensure patient safety and to review efficacy, evaluate recruitment, and assess overall data quality.

Medical Monitor- Responsible for providing medical guidance and overseeing patient safety for the study. The MM participates in determining the course of action necessary to meet safety goals and objectives. This is achieved through the review of safety reports; resolving safety issues; and interacting with Principal Investigators.

2. BACKGROUND INFORMATION AND SCIENTIFIC RATIONALE

2.1 Background Information

High-energy open fractures, blast, gunshot wound and crush injuries to the distal tibia, ankle, hind foot and midfoot are common challenges to military and civilian trauma surgeons¹⁻²⁰. Management of these injuries is complicated by soft tissue injury, ectopic bone, contamination, and neurovascular injuries. Surgical advances have increased capabilities for limb salvage¹¹⁻¹⁵. But while prosthetic advances and amputee rehabilitation have facilitated high level function following amputation¹⁶, similar advances in orthotics and rehabilitation for limb salvage patients have been nearly nonexistent. Orthotic options for limb salvage patients have mostly been limited to plastic posterior leaf spring ankle foot orthosis (AFOs). Many limb salvage patients have been unable to achieve their desired functional goals due to volumetric muscle loss¹⁷, ectopic bone, chronic pain and nerve injury^{8,13}. In the current military conflict, complications and the inability to achieve the desired level of activity have contributed to high rates of late amputation¹⁸⁻²⁰.

Current Orthotic Options. Ankle foot orthoses are frequently prescribed for patients with ankle dorsiflexion and plantarflexion weakness due to a variety of etiologies from cerebral palsy in children to trauma and stroke in adults. Numerous types of AFOs exist for different clinical scenarios, each with specific clinical goals for their use. In particular, AFOs are used to counteract both ankle plantarflexion and dorsiflexion weakness by providing support to the ankle joint to prevent excessive activation of the opposing muscle groups (i.e. to counteract large plantarflexion moment in dorsiflexion weakness, and large dorsiflexion moment with plantarflexion weakness). Patients with deficiencies in both of these muscle groups have significant challenges with normal gait, as they are unable to create the large torques and powers needed to overcome these limitations without assistance. Conventional rigid AFOs typically consist of a hard plastic mold extending from the metatarsal heads to the proximal leg. These place the ankle in a neutral position and help to prevent excessive plantarflexion during swing phase that may lead to a “steppage gait,” and ensure that the heel contacts the ground at initial strike (first rocker). These AFOs do not provide any assistance with plantarflexion, and cannot contribute to push-off at terminal stance (third rocker)³⁴⁻³⁷.

In an effort to provide more plantarflexion power, the “energy-storing AFO” was designed. The design typically involves a carbon fiber material at the posterior aspect of the AFO. Biomechanical data suggests that deformation of the carbon fiber spring which occurs during ankle dorsiflexion in stance (second rocker) is returned during the third rocker allowing for more powerful plantarflexion during step-off. The hope is these devices will allow patients with both plantarflexion and dorsiflexion weakness to have more normal ankle biomechanics and increased ankle power. This, in turn, may lead to increased gait velocity, decreased work of ambulation, and may allow the patient adequate power to run³⁴⁻³⁷. Energy-storing carbon fiber orthoses have been shown to improve abnormal gait patterns, temporal-spatial parameters, increase stride length, ankle power and range of motion in small series of patients³⁸⁻⁴¹. However, these studies largely address pediatric patients with cerebral palsy, myelomeningocele or other motor disorders, or adults with hemiplegia. No study to date has investigated the use of energy-storing orthoses in a traumatic limb salvage population.

The Intrepid Dynamic Exoskeletal Orthosis (IDEO) and Return to Run (RTR) Clinical Pathway.

The Intrepid Dynamic Exoskeletal Orthosis (IDEO) (**Figure 1**) is a custom, energy-storing carbon fiber orthosis specifically developed at the Center for the Intrepid, San Antonio Military Medical Center (SAMMC) for trauma patients undergoing limb salvage. The IDEO device is an FDA exempt device under 21 CFR 890.3475 and 21 CFR 890.3410. It incorporates a posteriorly mounted carbon fiber strut with a proximal ground reaction cuff and distal supramalleolar AFO. The proximal ground reaction cuff is a circumferential support fashioned in the style of a patellar tendon bearing prosthetic located at the proximal leg, with a posterior attachment to the proximal end of the carbon fiber strut. The distal supramalleolar AFO spans from the posterior attachment to the distal end of the carbon fiber strut, around the ankle joint and under to foot to the toes. A cushioned heel allows for shock absorption during the loading response. The laminated carbon fiber foot plate, which is inspired by prosthetic running feet, is rigid resulting in deformation primarily through the posteriorly positioned carbon fiber strut. This maximizes strut dynamics and power. The plantarflexed position of the footplate combined with a gradual roller shape allows for increased deflection and energy storage as the tibia progresses forward from mid to terminal stance. This also allows for forefoot loading during agility and running activities. The modular design allows for alignment adjustment, the ability to change strut stiffness based on individual patient strength gains, and facilitates donning and doffing to accommodate volumetric muscle changes from strength gains or edema. The IDEO will be labeled with the following information for use in this study: ***“CAUTION--Investigational device. Limited by Federal law to investigational use.”***

Figure 1: The IDEO

To maximize an individual's potential success in utilizing the IDEO, a high intensity, sports medicine based approach to rehabilitation was developed in collaboration with the departments of orthopaedics, physical therapy and orthotics/prosthetics at the Center for the Intrepid and the San Antonio Military Medical Center. The multidisciplinary Return to Run (RTR) clinical pathway focuses on strength, agility and speed with the goal of enabling patients to return to running, sports and military deployment^{21,23}. Running was chosen as a surrogate for the return to high level function based on the successes of amputation rehabilitation programs⁴². Also, working alongside similar patients who have been fitted with an IDEO provides a built-in support group and helps build self efficacy, which is one of the most important predictors of good outcomes and return to usual activity. The early success of this clinical pathway showed 80% return to running²³. In addition to success in high level rehabilitation goals, the RTR Clinical Pathway has returned wounded warriors to duty to include deployment^{21,43-44}.

Preliminary Studies to Support the Efficacy of the IDEO and RTR Clinical Pathway.

In a small study of 18 subjects with unilateral dorsiflexion and/or plantarflexion weakness, the functional performance of the IDEO was compared against two commercially available orthoses and no orthosis. All participants in this study also completed physical therapy component of the Return to Run Clinical Pathway. Performance wearing the IDEO was compared to that wearing the Allard BlueRocker™ (BR), a rigid plastic posterior leaf spring (PLS), and no brace (NONE)²². Subjects were evaluated on six functional tests wearing the IDEO, BR, PLS, and NONE. Brace order was randomized and 5 trials were completed for each measure. Performance was

significantly better in the IDEO on all functional measures compared to all other bracing conditions ($p < 0.004$), with the exception of the sit-to-stand five times, in which there was only a significant improvement against the BR ($p = 0.014$). The forty yard dash improved by 37% over the PLS and NONE, and by 28% over the BR. The BR demonstrated a significant improvement in the forty yard dash compared to NONE ($p = 0.033$), and self-selected walking velocity on level terrain over NONE and PLS ($p < 0.028$), but no significant difference was found between the PLS, BR and NONE in any other functional measure. This study did not, however, evaluate the impact on patient reported outcomes of the improvements in functional performance⁴³.

2.2 Rationale

The development of a new custom energy-storing ankle foot orthosis (AFO), the Intrepid Dynamic Exoskeletal Orthosis (IDEO), integrated with the RTR Clinical Pathway designed to optimize the patient's adaptation to the IDEO, may significantly improve limb salvage outcomes, reduce the number of delayed amputations, and provide both service members and civilians who undergo limb salvage a higher quality of life²¹⁻²⁴. While some initial studies point to the benefits of the IDEO, these studies were performed using a small number of patients treated at one military treatment facility (where the IDEO was developed and refined), using measures of functional performance assessed in a controlled environment²². Data are needed to replicate the positive results of this study at other military treatment facilities and provide evidence that improvements in performance translate into longer term improvements in functional outcomes and quality of life.

3. STUDY OBJECTIVES

3.1 Primary Objective

To assess immediate and long-term improvements in functional performance and self reported outcomes in patients who are currently one or more years out from a traumatic unilateral lower extremity injury at or below the knee and have chronic muscle weakness and/or limited range of motion at the ankle that translates into functional deficits that interfere with daily activities and overall quality of life.

3.2 Secondary Objectives

To document patterns of device use, use of ambulatory aids, shoe wear and patient reported satisfaction associated with the IDEO. Participants will be asked about their satisfaction with comfort, cosmesis, ease of use, and durability.

To assess the economic impact of the PRIORITI program by (i) measuring one-year costs associated with participation in PRIORITI and compare these costs to those projected under standard of care; and (ii) estimating lifetime cost-effectiveness of the PRIORITI program relative to standard of care.

3.3 Exploratory Objectives

N/A

[figure not shown]
4. STUDY OVERVIEW

The study is a clinical investigation (study) to evaluate the effectiveness of the IDEO, an investigational FDA-regulated medical device. The effectiveness of the PRIORITI program will be evaluated using a before-after study design where participants serve as their own controls. A total of 85 participants at military treatment facilities will be identified at least 1 or more years after their injury. To ensure we are enrolling a ‘stable’ population, we will exclude individuals whose fractures and soft tissues injuries are not healed at the time of screening or for whom additional surgery is planned within the next six months.

The study will be conducted by the Major Extremity Trauma Research Consortium (METRC) (www.metrc.org). Specifically, participants will be recruited, consented and evaluated at 3 of METRC’s core military sites.

The study procedures are summarized in the **Figure below**.

Figure 1: Overview of Study Procedures

At the time of enrollment into the study (T0), all participants (those who have screened eligible and have consented) will be asked to complete a battery of performance tests to measure their baseline assessments of strength, agility, speed and postural stability. They will also complete several standardized assessments of self-reported functional activity, participation in major usual activity and sports and leisure activities, presence of pain, and overall well being. At this time, basic information about the participants, their injury and their use of health and rehabilitation services in the previous year will be collected. After completing these baseline assessments, the Study Site Certified Prosthetist/Orthotist (CPO) will take a cast of the leg and other pertinent measures that are needed for fabrication of the IDEO. The CPO will then fabricate the IDEO brace locally. The final fabricated device given to each subject will be labeled with the following information: “*CAUTION--Investigational device. Limited by Federal law to investigational use.*”

During the following 2-4 weeks participants will engage in a home physical therapy (PT) program as directed by the study team. The length of the home physical therapy program is dependant on the time required to fabricate the IDEO™. The focus of the Pre-IDEO PT is conditioning and building self-efficacy. It will build on the principles of the Return to Run Clinical Pathway developed at the CFI.

Following 2-4 weeks of home PT (T1), the participant will be fitted with the IDEO and engage in four weeks of Post-IDEO PT at the study center. During these 4 weeks, adjustments to the brace will be made and the participants will learn how to optimize the use of the brace.

At the end of the four weeks of post-IDEO PT (T2), performance testing will be repeated and overall satisfaction with the device assessed. The purpose of these assessments is to measure any immediate gains in function. Participants will then be formally ‘discharged’ from the PRIORITI program. They will be given the number of the Study Site Orthotist to call if any concerns arise with the IDEO and its fit. The costs associated with all visits to the orthotist during the 12 month follow-up period will be covered by the study.

At 6 months following the completion of the PRIORITI program (T3), participants will be contacted by the Study Coordinator and asked to participate in a brief interview by phone. The main purpose of this phone call is to keep participants engaged in the study and motivate them to come back to the hospital for the final visit at 12 months. We will also use this opportunity to ask them questions about their functioning, satisfaction with the brace and use of services (overall and specific to the IDEO). This interview will last about 15 minutes. During the call the he coordinator will remind the participant of the 12 month follow up visit. If the participant is living outside of the research site area, the coordinator will inform the participant that travel expenses can be covered for the 12 month follow up visit. (See appendix K).

At 12 months following the completion of the PRIORITI program (T4), participants will be asked to return to the Study Center to repeat the performance tests and self reported measures of outcome and satisfaction with the IDEO. Additional questions regarding use of services (overall and specific to the IDEO) will also be asked.

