6.3.4 Participant Interviews at T3

- ALL ITEMS ASKED AT T2 PLUS:

- Short Musculoskeletal Function Assessment (SMFA)
- Veterans Health Survey (VR-12)
- Usual major activity status
- If working: Work Productivity (WPAI)
- Hospitalizations in past 6 months
- Use of Orthotic Services in past 6 months
- Use of PT/OT Services in past 6 months
- Use of other Services in past 6 months

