6.3.5 Participant Interviews at T4

- ALL ITEMS ASKED AT T3 PLUS:
- Income (past year)
- Health Insurance (current)
- Self Efficacy
- Multidimensional Scale of Perceived Support (MSPS)
- Activities- Paffenbarger Activity Scale (PPAQ)
- Brief Pain Inventory (BPI)
- Patient Health Questionnaire Dépression Scale (PHQ-9)
- Post Traumatic Stress Disorder using the PCL Checklist

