6.3.5 Final Study Visit

Participants will complete the study at month 12. Any ongoing SAE's will be followed to resolution. The study will cover the travel expenses for participants that have moved out of the area so that they can participate in the 12 month follow up visit. Expenses that will be covered include: transportation to and from the study center (airfare, bus fare or mileage reimbursement), lodging expense (up to 1 night, if needed), meal per diem of 50.00 per day (2 day maximum).

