6.4.1 Primary Endpoints

The primary endpoints are functional performance and self reported functioning as measured using the Short Form Musculoskeletal Assessment (SMFA) and the Veterans Health Survey (VR-12).

Functional Performance The performance test battery includes a dyad of a “less demanding” test and a “more demanding” test for three of the domains. At the study initiation visit, the treating surgeon will clinically evaluate the participant’s health, weight bearing and ambulatory status and will provide written approval in order to proceed with the performance tests. Prior to and during the performance tests, the participant will be reminded that he/she can stop these activities at any point if he/she feels unsafe. Participants in the study will complete the “less demanding” test first and, if the score meets a critical threshold, they will move on to complete the “more demanding” test. This approach will provide information on higher level functioning without risking the safety of those with significant impairment. These dyads are summarized in the table below.

Details of each of these assessments are provided below.

- The Four Square Step Test (FSST)** is a dynamic test of balance and agility. It requires participants to rapidly change direction while stepping forward, backward, and sideways, over a low obstacle⁵⁴. The test has demonstrated reliability and validity through correlation with existing balance tests and a positive predictive value of 86%⁵⁴. The FSST does not require any special equipment and requires little space, and is timed using a stopwatch. Raters place four canes (or piping) in a cross on the floor (all four canes lay flat on the floor). The participant then steps as fast as possible into each square in a designated sequence (see Figure 3).
- The Illinois Agility Test**⁵⁴ is a commonly used test to measure agility by requiring the patient to turn in different directions and at different angles. The test requires the patient to

[figure not shown]

Figure 3: the Four Square Step Test

navigate through a series of cones placed 3.3 meters apart as quickly as possible. It is simple test to administer and requires little equipment. The test is timed using a stopwatch and requires 10 meters of length, 5 meters of width, and 8 cones (or markers of some kind).

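### No remote fallback is written for the one-year SMFA and VR-12, both primary endpoints, although the protocol already collects both by phone at six months

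*Combined protocol and SAP*

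**What the plan says.** Section 6.4.1 makes functional performance, the SMFA and the VR-12 the primary endpoints. It places the self-reported measures at T0 and T4, and Aim 2b tests T4 against T0.

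Section 4 describes the two late contacts differently:

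- At T3 (six months), "participants will be contacted by the Study Coordinator and asked to participate in a brief interview by phone". The call takes about 15 minutes. Section 6.3.4 (Participant Interviews at T3) lists the SMFA, VR-12, usual activity status, WPAI and service use among its items.
- At T4 (12 months), "participants will be asked to return to the Study Center to repeat the performance tests and self reported measures of outcome".

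The T4 interview list in section 6.3.5 opens with "ALL ITEMS ASKED AT T3 PLUS", so it carries the SMFA and VR-12 forward. Neither that list nor Appendix C names a mode. Section 6.1.1 also includes the SMFA in a telephone screen.

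Several provisions bear on attendance at T4:

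- Section 6.3.5 (Final Study Visit): "The study will cover the travel expenses for participants that have moved out of the area".
- Section 6.3.4 (Retention): payments for participants not on active duty, and contact and reminders through the year.
- Section 6.3.6: T4 procedures at an early termination visit where possible.
- Section 10.4: ten conduct measures against missing data, followed by missing-at-random, pattern-mixture and selection analyses.

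None of these is remote collection of the T4 forms.

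**The concern.** The SMFA and VR-12 do not need the participant on site, and the protocol accepts that at T3. The T4 performance tests do need attendance. Because T4 is written as a single site visit, a participant who misses the performance tests also loses two primary outcomes that a call could have captured.

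Two things are at stake. Pairs are lost for Aim 2b. More importantly, missing T4 may be related to outcome. Background section 2.1 reports that "the RTR Clinical Pathway has returned wounded warriors to duty to include deployment", so some non-attenders could be people doing well elsewhere; others could have given up the brace. With one group and no control arm, there is no second arm in which such a bias could cancel.

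Aim 4 is touched as well. The service-use questions look back six months, so a missed T4 leaves the second half of the 12-month cost period unobserved, along with the one-year VR-12 from which the VR-6D utility is computed.

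**Working it through.** **Inputs from section 10.2.** 85 enrolled; 80 assumed complete (5/85 = 5.9% lost); one-sided paired t-test; standardized change d = 0.28; 80% power. Alpha is not stated.

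**Reproducing the plan's figure.** Power = 1 − F(t(1−α, n−1)), where F is the noncentral t distribution with n − 1 degrees of freedom and noncentrality d√n. With n = 80, d = 0.28 and one-sided α = 0.05, power is 79.9%. The normal approximation, Φ(0.28 × √80 − 1.645), gives 80.5%. With one-sided α = 0.025, power is 69.6%. The stated 80% therefore fits one-sided 5%, which is used below as an assumption.

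**Losing T4 self-reports.** The documents give no rate of T4 non-attendance. The range below is assumed and replaces the planned 5.9% rather than adding to it.

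| Missing at T4 | Pairs left of 85 | Power at 0.28 | Effect detectable with 80% power |
|---|---|---|---|
| 5.9% (plan) | 80 | 79.9% | 0.280 |
| 10% | 76 | 78% | 0.288 |
| 15% | 72 | 76% | 0.296 |
| 20% | 68 | 74% | 0.305 |

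If a phone call recovered 80% of those missed (assumed), 85 × (1 − 0.10 × 0.20) ≈ 83 pairs would remain at 10% missing and 85 × (1 − 0.20 × 0.20) ≈ 82 at 20%, with power about 81% in both cases. The gain in power is modest.

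**Bias in the unadjusted mean.** Let f be the share missing and k the gap in mean change between attenders and non-attenders, in SDs of change. The completer mean minus the full-cohort mean is m_A − [(1 − f)m_A + f·m_N] = f(m_A − m_N), which has size f × k. For an assumed k = 0.5:

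- f = 10%: 0.10 × 0.5 = 0.05 SD, and 0.05/0.28 = 18% of the planned effect.
- f = 20%: 0.20 × 0.5 = 0.10 SD, and 0.10/0.28 = 36% of the planned effect.

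The sign of k is unknown. The figure applies to the unadjusted paired t-test that section 10.6 names for Aims 1 and 2, not to the missing-at-random analyses of section 10.4.

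**The case against.** **A reader might infer that the protocol rules out a phone T4.** It does not; it is silent. The PHQ-9 safety script in section 6.2.3 has a branch for phone interviews, yet the PHQ-9 is scheduled only at T0 and T4 and T0 follows in-person consent. That suggests phone interviews were contemplated. It is still not an instruction to collect the T4 SMFA and VR-12 by phone, and without one the sites may act differently. The manual of operations or the case report forms may say more, and they are worth checking.

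**A reader might infer that travel money is the only safeguard.** That is wrong. Section 10.4 pays investigators by follow-ups completed, monitors missing-data rates and sets site targets; section 6.3.4 keeps contact through the year; section 6.3.6 provides an early termination visit. These raise attendance. They do not supply a one-year value for someone who cannot come, and an early termination value is not a one-year value.

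**A reader might infer a known direction of bias, with deployed successes missing.** The documents do not support this. The deployment statement is background on earlier experience, no share on active duty is given, and participants who gave up the brace would pull the other way. T4 travel support is not limited to those off active duty, and someone deployed might not be reachable by phone either.

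**The planned analyses help.** T3 scores are natural auxiliary data under missing at random. This stands as mitigation, but those models estimate a value that a call could observe.

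**The fix has downsides.** A phone T4 set against an in-person baseline may carry a mode effect into the paired change, and a phone option offered freely could reduce attendance for the performance tests, which are equally primary. Both stand, and they limit how the fix should be worded.

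**Conclusion.** The point holds as a cheap improvement to the design. The only written T4 procedure is a site visit, and there is no written remote fallback for two primary endpoints that the protocol already takes by phone at T3.

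The power loss is small: about 2 to 6 points for assumed non-attendance of 10% to 20% at an assumed one-sided 5%. The stronger reason is possible bias in the one-year self-report change, equal to the missing share times an unknown gap. The 0.05 to 0.10 SD shown is an example resting on an assumed 0.5 SD gap. It is not a forecast, and its direction is unknown. If losses stay near the planned 5.9%, the effect on power is nil and the bias is small unless the gap is large.

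**What to change.** In section 4, in both sections numbered 6.3.5 (Participant Interviews at T4; Final Study Visit) and in a footnote to Appendix C, add a rule to this effect: if in-person T4 cannot be achieved within the visit window after the usual efforts, the coordinator collects the SMFA, VR-12, usual activity status, WPAI and service use by phone as at T3, records the mode, and the data count as T4. State that the call is to be made before the window closes, since section 6.3 ties inclusion in the database to that window.

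Word it as a last resort and not as an alternative offered to participants, to protect attendance for the performance tests. In section 10.4 or 10.6, add a sensitivity analysis of the one-year SMFA and VR-12 that leaves out phone T4s.

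The cost is a short protocol amendment, a mode field on the T4 form, and a call by the coordinator who already makes the T3 call. The T4 performance tests and clinical assessment would still be missing for these participants.
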